6.3 Early Termination and Withdrawal Assessments

Data collected from early termination/withdrawal visits apply to the analysis as follows.

- Efficacy endpoints
 - In accordance with section 6.2, analysis is performed as result of a regular visit only when it comes within the visit window corresponding to each regular visit.
- Safety endpoints
 - It is excluded from the analysis of regular visits but will be presented in the listing.
 - If early termination/withdrawal visit is the last visit, the result value will be summarized as final visit.

6.4 Repeated or Unscheduled Assessments

In accordance with section 5.6, if there is more than one result prior to the first IP administration, the latest result before the first IP administration will be considered as a baseline.

In case there are measurements from an unscheduled visit after the first dose of IP, measurements at scheduled and unscheduled visit are chronologically presented in the subject list whereas summary of descriptive statistic by time point will only include measurements at scheduled visits. If two or more data within same visit window exist, the value from regular visit will be used for analysis.

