10.3 Clinical Laboratory Analyses

10.3.1 Variable, Definition and/or Derivation

Laboratory Tests*	Variables
Hematology test, Blood chemistry test	Change from baseline at week n = result at week n – result at baseline n=6, 14, 26
	Change from baseline at final visit result at final visit* – result at baseline *the last visit among regular visit, unscheduled visit and End visit/Drop out visit.
Hematology test, Blood chemistry test, Urinalysis test	Normality - Normal - Abnormal NCS - Abnormal CS
	Shift from baseline to week n, n=6, 14, 26 - Normal or Abnormal NCS - Abnormal CS
	Shift from baseline to final visit - Normal or Abnormal NCS - Abnormal CS

* The laboratory tests will include following test items.

Laboratory Test	Laboratory Test Items(unit)
Hematology test	- WBC ($10^3/\mu\text{L}$) - RBC ($10^6/\mu\text{L}$) - Hemoglobin (g/dL) - Hematocrit (%) - Platelet count ($10^3/\mu\text{L}$) - Neutrophils (%) - Lymphocytes (%) - Monocytes (%) - Eosinophils (%) - Basophils (%)
Blood chemistry test	- BUN (mg/dL) - Creatinine (mg/dL) - Uric acid (mg/dL)

Laboratory Test	Laboratory Test Items(unit)
	
 - Total bilirubin (mg/dL) - Albumin (g/dL) - Total protein (g/dL) - ALT(IU/L) - AST(IU/L) - γ-GTP(IU/L) - Alkaline phosphatase (IU/L) - Glucose (mg/dL) - Total cholesterol (mg/dL)
Urinalysis test	
 - Protein (Albumin) - Glucose - Ketones - WBC - Blood (RBC)

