10.3.2 Method of Analysis

Actual values and changes from baseline for continuous clinical laboratory test results will be summarized by treatment group at each time point using descriptive statistics (number of subjects observed, mean, standard deviation, median, minimum, and maximum). In addition, depending on whether the assumption of normality is satisfied, the intragroup comparison will use the paired t-test or Wilcoxon's signed-rank test, while the intergroup comparison (GV1001 0.56 mg/day vs. control group, GV1001 1.12 mg/day vs. control group) will use the two-sample t-test or Wilcoxon's rank-sum test to perform analysis.

For categorical variables, shift tables from baseline visit to each scheduled post-baseline visit, will be generated for clinical laboratory test results using Normal or Abnormal not clinically significant (NCS)/Abnormal clinically significant (CS), by treatment group and overall subjects. The intragroup comparison will use McNemar's test, while the intergroup comparison (GV1001 0.56 mg/day vs. control group, GV1001 1.12 mg/day vs. control group) will use Pearson's chi-square test or Fisher's exact test to perform analysis.

Subjects with normal or abnormal NCS values at baseline that shifted to abnormal CS after baseline on laboratory test will be listed.

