10.4.2 Electrocardiogram

10.4.2.1 Variable, Definition and/or Derivation

Electrocardiogram	Variables
Overall interpretation	Normality - Normal - Abnormal NCS - Abnormal CS
	Shift from baseline to week n, n=14, 26 - Normal or Abnormal NCS - Abnormal CS
	Shift from baseline to final visit - Normal or Abnormal NCS - Abnormal CS

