10.2.11. Unscheduled Visits

Additional visits may be made from time to time, outside of the scheduled visits, at the request of the subject or the subject's representative or as deemed necessary based on the judgment of the investigator. To this end, the investigator shall inform the subjects of this during their regular visits to the study site, and ensure that the subjects immediately contact the investigator if any adverse events should occur. The visit schedule shall not be changed because of the unscheduled visits. At unscheduled visits, examinations and tests may be performed at the discretion of the investigator.

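### No worst-post-baseline shift is planned for laboratory tests or ECG, so a transient clinically significant result seen only at an unscheduled test enters no shift table or shift comparison between arms

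*SAP*

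**What the plan says.** Four parts of the SAP, and one of the protocol, settle which results reach the laboratory and ECG shift analyses.

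- **Unscheduled results.** SAP 6.4 puts post-dose unscheduled measurements in the subject list, while the "summary of descriptive statistic by time point will only include measurements at scheduled visits". Protocol 10.2.11 leaves such testing open: "At unscheduled visits, examinations and tests may be performed at the discretion of the investigator".
- **Exit results.** For safety data from an early termination or withdrawal visit, SAP 6.3 says "It is excluded from the analysis of regular visits but will be presented in the listing". It then adds: "If early termination/withdrawal visit is the last visit, the result value will be summarized as final visit".
- **Laboratory.** SAP 10.3.1 defines "Shift from baseline to week n, n=6, 14, 26" and also a shift to the final visit, which is "the last visit among regular visit, unscheduled visit and End visit/Drop out visit". SAP 10.3.2 describes "shift tables from baseline visit to each scheduled post-baseline visit", with McNemar's test within arms and a chi-square or Fisher test for each dose against control.
- **ECG.** SAP 10.4.2.1 defines "Shift from baseline to week n, n=14, 26" and a shift to the final visit. SAP 10.4.2.2 plans the same kinds of test.

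SAP 10.3.2 and 10.4.2.2 also list every subject who moves from normal or abnormal NCS at baseline to abnormal CS afterwards. The SAP text defines no shift to the worst, or to any, post-baseline result.

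**The concern.** Evaluating safety is part of the primary objective. After the first dose there are only three scheduled laboratory time points and two scheduled ECGs. Protocol 10.2.11 has subjects contact the investigator at once if an adverse event occurs, so an extra test is often likely to be done because something seems wrong. A short-lived abnormality is most likely to be picked up at such a test, and these results are kept out of the by-visit shifts.

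If one dose caused transient abnormalities that cleared before the next scheduled test, the laboratory and ECG shift comparisons could look alike across arms although the data held the difference. With 25 subjects enrolled per arm, a few uncounted subjects can change how a shift table reads.

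**Working it through.** **1. When the scheduled tests fall.** The nominal study day is 7 × (week − 1) + 1.

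- Week 6: 7 × 5 + 1 = 36
- Week 14: 7 × 13 + 1 = 92
- Week 26: 7 × 25 + 1 = 176

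These are the centres of the SAP 6.2 windows (31–41, 87–97 and 171–181). Counted from Day 1, the laboratory gaps are 35, 56 and 84 days and the ECG gaps are 91 and 84 days.

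**2. Where each kind of abnormal CS result is counted**, reading SAP 6.3, 6.4, 10.3 and 10.4.2 together:

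| Abnormal CS result | By-visit shift | Final-visit shift | CS listing |
|---|---|---|---|
| At a scheduled test | Yes | If last | Yes |
| First at an unscheduled test, still present at the next scheduled test | Yes | If last | Yes |
| At an exit visit that is the last visit | No | Yes | Yes |
| At an unscheduled test that is the last result | No | Yes | Yes |
| Only at an unscheduled test, resolved by the next scheduled test, not the last result | **No** | **No** | Yes |

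Only the last row is a gap. SAP 10.4.2.1 does not define final visit again for ECG, and the shift-table sentence in SAP 10.3.2 does not mention the final-visit shift. I have assumed that the SAP 10.3.1 definition applies to both and that the shift is produced.

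**3. How large the gap could be.** The documents give no rate of unscheduled testing and no duration of abnormalities, so only a ceiling can be shown, and only under assumptions. Assume onset uniform over Days 2–176 (175 days), a duration of L days, and k scheduled tests on their nominal days. While the intervals do not run into each other or past Day 2, the share that meets no scheduled test is 1 − kL/175.

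| L (days) | Laboratory, k = 3 | ECG, k = 2 |
|---|---|---|
| 7 | 1 − 21/175 = 88% | 1 − 14/175 = 92% |
| 14 | 1 − 42/175 = 76% | 1 − 28/175 = 84% |
| 28 | 1 − 84/175 = 52% | 1 − 56/175 = 68% |
| 56 | 1 − (35 + 56 + 56)/175 = 16% | 1 − 112/175 = 36% |

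In the last laboratory cell, only 35 onset days (Days 2–36) precede the Day 36 test, so 35 replaces 56.

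These figures measure how sparse the scheduled tests are. They do not measure the loss from leaving out unscheduled results. To fall in the gap, an abnormality must also be caught by an unscheduled test while present. If that happens with probability u, the affected share is at most u times the figure shown. The documents do not give u, so for a 14-day laboratory abnormality the range runs from 0 (u = 0) to 76% (u = 1).

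**The case against.** **The safeguards already planned.** The final-visit shift takes in exit and unscheduled results when they come last. Protocol 5.5.1 asks dropouts to attend a last time for the Visit 16 tests, so an exit test will usually be the last result and will be tabulated. A reader of SAP 6.3 might infer that exit results are lost to the arm comparisons. They are not. This part of the objection stands in full.

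**Listings and adverse events.** Every shift to abnormal CS is listed. The adverse event definition in SAP 10.2.1 includes abnormal laboratory results, SAP 10.2.2.2 and protocol 11.2.10.1 present events by SOC and PT, and overall incidence is tested between arms. A reported abnormality does therefore appear by arm. This stands in part. A listing gives no rate. The adverse event route depends on the investigator reporting the finding, and protocol 10.5.2 asks for an overall diagnosis in place of separate signs, so the laboratory or ECG result may not appear under its own term. Neither is a shift comparison for that test.

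**Size.** A reader might infer from the ceilings above that half or more of such abnormalities are dropped by the plan. The documents do not support that: an abnormality that nobody tests for is missed under any table, and the durations are assumed. It is also tempting to picture 6 of 25 on a dose against 0 of 25 on control (Fisher p = 0.022) being tabulated as 0 against 0. That needs all six to miss every scheduled test. On the same assumptions, for durations of 14 and 28 days, the chance is 0.76⁶ = 19% and 0.52⁶ = 2% for laboratory tests, and 0.84⁶ = 35% and 0.68⁶ = 10% for ECG. It is a constructed extreme and shows only the mechanism.

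**Design.** Scheduled-only tables protect by-visit comparisons from unequal discretionary testing. That is a good reason to keep them, and none against adding a table beside them. The mock-up tables in SAP Appendix 1 are not shown, so a suitable shell may exist, but the SAP text defines no such variable.

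**Conclusion.** The point holds in a narrow form. A clinically significant laboratory or ECG abnormality found only at an unscheduled test, resolved by the next scheduled test and not the subject's last result, enters no shift table and no shift comparison between arms. It remains visible in the listing and, if reported, among the adverse events.

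This follows from the SAP wording and needs no numerical assumption beyond reading final visit for ECG as it is defined for laboratory tests. The frequency is unknown, and the ceilings in the working are illustration only.

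It would be too strong to say that unscheduled and exit results are shut out of all safety comparisons. The final-visit shift and the adverse event tables contradict that. The point is worth acting on because safety is part of the primary objective and the missing table can be built from data already collected.

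**What to change.** Keep the by-visit and final-visit tables as they are. Add to SAP 10.3 (hematology, blood chemistry, urinalysis) and SAP 10.4.2 (ECG) a shift from baseline to the worst post-baseline result, using all post-dose results: scheduled, unscheduled and exit. With the SAP's two shift categories, worst means abnormal CS at any post-dose test. Compare each dose with control by the chi-square or Fisher test already specified.

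Show the number of tests per subject by arm beside each table. This addresses the one real downside: subjects tested more often have more chances to show an abnormality, so unequal testing between arms could produce a difference.

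A short cross-reference in SAP 6.4 to the new table is enough. SAP 6.3 and 6.4 already confine their exclusions to regular-visit and by-time-point analyses, so they need no other change. The cost is SAP wording and one extra table per domain, with no new data and no change to study procedures.

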6.5 Handling of Incomplete Dates

For AE data, in case day or month is omitted from the start date, only collected date units will be used without any imputation of date. When the entire start date is missing or the format of the collected AE date does not allow for comparison, the AE will be assumed to be TEAE.

For medication, in case day or month is omitted from the start or end date thus collected as 'UK', only collected date units will be used without any imputation of date. When the entire start date is missing or the format of the collected start date does not allow for comparison with the first IP administration date, the medication is assumed to be used prior to the first dose administration date of the investigational product.

6.6 Character Values of Clinical Laboratory Variables

In summary of laboratory data, minimum or maximum value will be used if value includes inequality sign (ex. use 4 for ' ≥ 4 or > 4 ' and use 100 for ' ≤ 100 or < 100 '). When listing the results for subjects, the values recorded in eCRF (such as value with inequality sign) will be presented.

7. ANALYSIS SETS

The main analysis of efficacy evaluation of this clinical study will be performed on the full analysis set (FAS) and the analysis on the per-protocol set (PPS) will be performed as a supplement. The safety evaluation analysis will be performed as actually administered in the safety set. The exploratory evaluation analysis will be performed on the FAS and PPS, and the demographic and the characteristics prior to administration will be analyzed for Randomized Set.

7.1 Screened Set

The screened set is defined as subjects who sign the informed consent form and are assigned a screening number.

7.2 Randomized Set

Randomized set consists of data from all subjects who are randomized into the study.

7.3 Full Analysis Set (FAS)

This includes subjects who received at least 1 dose of the investigational product after randomization and had at least 1 evaluation with the PSP-rating scale after the administration of the investigational product and up to the end of the clinical study. In the FAS, subjects will be included in the group to which they were randomized.

7.4 Per-Protocol Set (PPS)

Among the subjects included in FAS, the subjects who completed the clinical study without major protocol violations are included. Subjects with major protocol violations (see 5.5.3 Protocol Violations section in the protocol) may be excluded from PPS.

Exclusion from PPS will be decided through a blind meeting prior to database lock, after comprehensively discussing whether the clinical study was affected.

7.5 Safety Set

Among the subjects who were administered at least one dose of the investigational product after randomization, subjects whose safety-related data were evaluated at least once after the administration will be included.

8. STUDY POPULATION ANALYSES

8.1 Subject Disposition

The disposition of all screened subjects will be summarized for overall subject (total) and by treatment group.

For the screened set, the number of screened subjects, screened failed subjects, and the reasons for screening failure will be summarized by overall subject. For the Randomized set, the number of subjects who are randomized and the number and percentage (%) of subjects who are treated/not treated and completed/early termination will be summarized by treatment group and overall subject. The number of the reasons for discontinuation also will be presented by treatment group and overall subjects. Subject disposition will be presented as a summary table and a figure. Also, screening failed subjects and discontinued subjects will be listed.

8.2 Important Protocol Deviations

For the Randomized set, important protocol deviations will be summarized as the number of subjects, percentage (%), and the number of events by treatment group and overall. Also, important protocol deviation data will be listed.

8.3 Analysis Set

For all subjects in Randomized set, Subjects in each analysis set (Safety set, FAS and PPS) will be summarized with counts and percent for overall subject and by treatment group. The reason excluded from each analysis set will be summarized with count for overall subject and by treatment group. Subjects exclude from each analysis set will be listed.

8.4 Demographic

8.4.1 Variable, Definition and/or Derivation

Demographic will be presented by treatment group.

Variables	Unit or Categories
Age	Years
Age group	
• < 65 years• ≥ 65 years
Derivation Method:	
eCRF [Demographics] page에 기재된 Age를 기준으로 실제 연령 그룹으로 분류	
Sex	
• Male• Female
Baseline BMI	kg/m ²

Variables	Unit or Categories
Derivation Method:	
Baseline Body Weight (kg) / (Baseline Height (cm) x 0.01) ²	
Fertility	
 • Yes • No • Perform serum FSH test
Menopause	
 • Yes • No
Duration of PSP	months
Derivation Method:	
(Randomization Date – Diagnosis Date + 1) x 12 / 365.25	
- If day or month is omitted from the first date of diagnosis, will be using "01" imputation of date. If year is omitted from the first date of diagnosis, the subject will be excluded from the analysis.	
PSP Type	
 • Richardson type [PSP-RS] • Parkinsonian type [PSP-p]

8.4.2 Method of Analysis

For the Randomized Set, Demographics will be summarized using descriptive statistics by treatment group and overall subject (total). Continuous variables will present the number of subjects observed, mean, standard deviation, median, minimum, and maximum. In addition, depending on whether the assumption of normality is satisfied, the two-sample t-test (if normality assumption is satisfied) or Wilcoxon's rank-sum test (if normality assumption is not satisfied) will be used to compare each study group with the control group (GV1001 0.56 mg/day vs. control group, GV1001 1.12 mg/day vs. control group). Categorical variables will present frequencies and percentages, and depending on whether cells with an expected frequency less than 5 exceed 20% of the total cells, Pearson's chi-square test (if the cells with an expected frequency less than 5 does not exceed 20% of the total cells) or Fisher's exact test (if the cells with an expected frequency less than 5 exceed 20% of the total cells) will be used to compare each study group with the control group (GV1001 0.56 mg/day vs. control group, GV1001 1.12 mg/day vs. control group).

For the Randomized Set, demographics and baseline characteristics data will be listed.

8.5 Medical History and Concurrent Disease

8.5.1 Variable, Definition and/or Derivation

All medical histories will be classified as medical history and concurrent disease according to the following criteria.

Variables	Definition and/or Derivation
Medical History	Maintenance='No' on the [Medical/Surgical History] page of eCRF.
Concurrent Disease	Maintenance='Yes' on the [Medical/Surgical History] page of eCRF.

8.5.2 Method of Analysis

All medical histories will be classified as medical history and concurrent disease and summarized by treatment group and overall subjects in the Randomized Set. The number and percentage (%) of subjects and the number of cases will be presented based on Preferred Term (PT) and System Organ Class (SOC).

Medical/surgical history and concurrent disease will be listed for Randomized set.

8.6 Prior and Concomitant Medication

8.6.1 Variable, Definition and/or Derivation

All medications will be classified as prior and concomitant medication/therapies according to the following criteria.

Variables	Definition and/or Derivation
Prior Medication	- The end date is prior to the date of the first IP administration (The end date < the date of the first IP administration)
Concomitant Medication	- The start date is on or after the date of the first IP administration and on or before the date of End of Study; or (The date of the first IP administration \leq the start date \leq the date of End of Study) - The start date is on or before the date of the first IP administration, but the end date is on or after the date of the first IP administration; or (The start date \leq the date of the first IP administration, and -the end date \geq the date of the first IP administration) - The end date is ongoing. (‘ongoing’ is checked on [Prior/Concomitant Medications] page of eCRF)

If the start or end date is missing or incomplete and the prior/concomitant medications cannot be distinguished, they will be classified as concomitant medications.

8.6.2 Method of Analysis

All medications will be classified as prior and concomitant medications and summarized by treatment group in the Randomized Set. The number and percentage (%) of subjects and the number of cases will be presented based on ‘Anatomical main group (level 1)’, ‘Therapeutic subgroup (level 2)’ for overall subject and by treatment group.

Prior and concomitant medication will be listed for Randomized Set.

8.7 Drug Compliance

8.7.1 Variable, Definition and/or Derivation

Variables(unit)	Definition and/or Derivation
Drug compliance (%)	$\frac{\text{Actual number of doses administered (injections)}}{\text{Number of doses that should be administered (injections)}} \times 100$ Number of doses that should be administered (injections) = (i) 14, if the subject completes the study (ii) Number of planned injections before discontinuations

8.7.2 Method of Analysis

For the Randomized Set, drug compliance will be summarized using descriptive statistics (the number of subjects, mean, standard deviation, median, minimum and maximum) by treatment group and overall subject (total).

Drug compliance data will be listed for Safety Set.

9. EFFICACY ANALYSES

9.1 Primary Efficacy Endpoint(s)

9.1.1 Variable, Definition and/or Derivation

Change from the baseline in the total score of PSP-rating scale after 24 weeks (6 months)

- Change from baseline at week 24 = week 24 – baseline

9.1.2 Method of Analysis

Descriptive statistics (number of subjects observed, mean, standard deviation, median, minimum, and maximum) will be presented by treatment group for each visit and the change from the baseline in the total score of the PSP-rating scale after 24 weeks (6 months) of investigational product administration. To test the difference between each study group and the control group (GV1001 0.56 mg/day vs. control group, GV1001 1.12 mg/day vs. control group), an MMRM analysis will be conducted with the treatment groups, visits, and interactions between the visits and the treatment groups set as fixed effects, and the subjects set as the random effect, as well as considering the baseline values, age, and sex as covariates. The results of the MMRM analysis will be summarized by LSM and standard error (SE) for each treatment group, the LSM difference between the study groups and the control group (GV1001 0.56 mg/day vs. control group, GV1001 1.12 mg/day vs. control group) and its 95% confidence interval as well as the two-side p-value.

Additionally, testing the difference within each treatment group will be conducted by the same MMRM analysis.

MMRM constructed as follows

- Dependent Variable: Change from baseline in total score of PSP-rating
- Fixed Effects
 - Fixed Continuous Effects: Baseline PSP-rating, Age
 - Fixed Categorical Effects: Treatment, Visit, Visit*Treatment, Sex
- Repeated Effect: Visit
- Random Effect: Subject
- Covariance Structure: Unstructured (UN)

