3.5 Changes to Analysis from Protocol

Protocol Language	SAP Language Changed from Protocol	Reason of Change				
none	9.2.7 Change from the baseline in the total score of modified PSP-rating scale 10 after 12 weeks (3 months) and 24 weeks (6 months) of investigational product administration (...)	Add extra secondary efficacy endpoint for further exploration of efficacy				
none	9.2.8 Change from the baseline in the total score of modified PSP-rating scale 14 after 12 weeks (3 months) and 24 weeks (6 months) of investigational product administration (...)	Add extra secondary efficacy endpoint for further exploration of efficacy				
none	9.2.9 Proportion of subjects with change from the baseline in the total score of PSP-rating scale ≤ 0 after 24 weeks (6 months) of investigational product administration [Subgroup: Richardson type] (...)	Add extra secondary efficacy endpoint for further exploration of efficacy				
none	9.2.10 Proportion of subjects with change from the baseline in the total score of Modified PSP-rating scale 10 ≤ 0 after 24 weeks (6 months) of investigational product administration [Subgroup: Richardson type] (...)	Add extra secondary efficacy endpoint for further exploration of efficacy				
none	9.2.11 Proportion of subjects with change from the baseline in the total score of Modified PSP-rating scale 14 ≤ 0 after 24 weeks (6 months) of investigational product administration [Subgroup: Richardson type] (...)	Add extra secondary efficacy endpoint for further exploration of efficacy				
11.2.6. Subgroup Analysis Subgroup analysis will not be considered in this clinical study.	
11. SUBGROUP ANALYSES Subgroup analyses for efficacy will be conducted on the endpoint related with PSP-rating scale, modified PSP-rating scale 10 and modified PSP-rating scale 14 for FAS using the same analysis methods (refer to 9.1 and 9.2).
 
  
 Subgroup Variable	Category	
   
 PSP Type	 
 Richardson type [PSP-RS] Parkinsonian type [PSP-p] 	
  
	Subgroup Variable	Category	PSP Type	
 Richardson type [PSP-RS] Parkinsonian type [PSP-p] 	Add subgroup analysis for further exploration of efficacy
Subgroup Variable	Category					
PSP Type	
 Richardson type [PSP-RS] Parkinsonian type [PSP-p] 					

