12. SENSITIVITY ANALYSES

Sensitivity analysis will not be considered in this clinical study.

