6.2. Design of Clinical Study

[figure not shown]
This is a 24-week, multicenter, randomized, double-blind, placebo-controlled, parallel design, prospective, Phase 2a exploratory clinical study.

If the subject and/or the subject's representative provide a written consent to participate in this clinical study, the required examinations and tests will be performed at the screening visit, and the screening period will run for 4 weeks or shorter.

Subjects who are ultimately determined as eligible by the inclusion/exclusion criteria after screening will be randomized at a 1:1:1 ratio to Study Group 1 (GV1001 0.56 mg/day), Study Group 2 (GV1001 1.12 mg/day), or the placebo group depending on the study site in which they are enrolled. Depending on the randomization results, subjects will be administered the investigational product (study drug or placebo) once weekly for the first 4 weeks (1 month), and then administered 10 times at 2-week intervals for 20 weeks (5 months) for a total of 14 doses over 24 weeks (6 months).

All subjects will visit the study site according to the planned clinical study schedule to receive the investigational product and to be evaluated for efficacy and safety. To ensure the objectivity and accuracy of the study results, the efficacy evaluators evaluating the PSP-rating scale will be limited to neurologists who have been sufficiently educated and trained, and the collection of efficacy and safety evaluation data and biomarkers will be performed in a consistent order at each visit.

※ Neurological drugs administered at a stable dose for at least 1 month prior to a subject's participation in this clinical study (prior to screening) will be continued without changing the dose during the clinical study participation period.

[Clinical Study Schematic]

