6.3. Randomization

Subjects who provide a written consent to participate in this clinical study will be assigned a screening number consisting of [study site number: 2 digits]-S-[serial number: 3 digits] in the order in which the written consent was obtained. Subjects who meet the inclusion and exclusion criteria will then be randomized according to the randomization plan, and will be assigned a unique randomization number consisting of [study site number: 2 digits]-R-[serial number: 2 digits] in the order in which the investigator decided to enroll the subjects. Subjects who meet the inclusion and exclusion criteria will be assigned sequentially according to the order of randomization at each study site.

A randomization table will be generated by an independent statistician not related to this clinical study prior to the start of the clinical study by using SAS® (Version 9.4 or higher; SAS institute, Cary, NC, USA), and the table will be generated to allow assignment of subjects to Study Group 1, Study Group 2, or the control group at a 1:1:1 ratio by applying a stratified block randomization method. Subjects who are enrolled in this clinical study and ultimately determined to be eligible to participate in the clinical study will be assigned a randomization number sequentially through the Interactive Web Response System (IWRS), and afterward, the subjects will be assigned to Study Group 1, Study Group 2, or the control group and receive a unique IP number.

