11.2.3. Covariate Adjustment

Efficacy endpoints will be analyzed with adjustments for the baseline values as well as for the age and sex.

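### Randomisation appears to be blocked within study site, but no efficacy MMRM contains site and no sensitivity analysis is planned; if sites differ, the reported standard errors are too large

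*SAP*

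**What the plan says.** **Randomisation.** Protocol 6.3 describes a table that allocates subjects "at a 1:1:1 ratio by applying a stratified block randomization method". It does not say what the strata are. The same section has eligible subjects "assigned sequentially according to the order of randomization at each study site", and each randomisation number begins with the site number. Protocol 6.2 has subjects randomised to one of the two dose groups "or the placebo group depending on the study site in which they are enrolled"; SAP 3.2 repeats this. No other stratification factor appears in either document.

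**Analysis.** The primary MMRM in SAP 9.1.2 has "Fixed Categorical Effects: Treatment, Visit, Visit*Treatment, Sex", with baseline score and age as continuous terms. SAP 9.2.1.2 and 9.2.2.2 have the same structure, and the remaining change-score endpoints refer back to 9.2.2.2. This follows protocol 11.2.3: "Efficacy endpoints will be analyzed with adjustments for the baseline values as well as for the age and sex".

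**Handling of the stratum.** SAP 5.3, headed Stratifications, says only that none is planned. That may mean no more than that no stratified analysis is intended, but nothing else in the SAP says what happens to the randomisation stratum. SAP section 12 states: "Sensitivity analysis will not be considered in this clinical study". Section 13 excludes additional analyses too.

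**The concern.** When arms are balanced within site, differences between sites largely cancel out of the treatment comparison. The true sampling error is then smaller than it would be under unrestricted randomisation. A model without site does not use this: the between-site variation stays in the residual and inflates the reported SE. The treatment estimate remains unbiased, the interval is too wide and the test rejects too rarely.

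Protocol 11.4 and SAP 3.3 give the purpose of the trial as estimating an effect size, with about 20 analysable subjects per arm. The interval is therefore a main product of the study, and SAP 9.1.3 also attaches a superiority reading to p < 0.05. The primary outcome is a clinician-rated scale used at several sites, so some site difference in change is plausible, though the documents give no estimate of it. If no site-adjusted analysis is pre-specified, any later one will be post hoc.

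**Working it through.** **The plan's own figure.** SAP 3.3 has 20 evaluable subjects per group and 20% dropout: 20 / (1 - 0.20) = 25 per group, and 3 x 25 = 75. This reproduces. No SD, effect size or power is stated.

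**Inputs that are assumed.** The documents do not give the number of sites, the block size or the share of the variance in change that lies between sites (call it r). The check therefore covers ranges of each.

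**Large-sample limit.** With n per arm, total SD s and exact balance within site:

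- SE reported without site: s x sqrt(2/n). At n = 20 this is 0.316s.
- True SE: s x sqrt(2(1 - r)/n). At n = 20 this is 0.300s for r = 0.10 and 0.283s for r = 0.20.
- Ratio: 1/sqrt(1 - r), which is 1.054 for r = 0.10 and 1.118 for r = 0.20.
- Actual two-sided alpha: 2[1 - Phi(1.96 x ratio)], which is about 0.039 and 0.028.

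**Simulation.** Incomplete blocks and dropout weaken the balance, so the limits overstate the effect. The simulation used 75 subjects randomised 1:1:1 in permuted blocks of 3 or 6 within 5, 8 or 12 unequal sites, with 0% or 20% random dropout. There were 36 settings with 12,000 trials each. Week-24 change was fitted on treatment and three covariates, with and without site; sites with fewer than 6 analysed subjects were pooled. The ratios do not depend on the SD. The Monte Carlo SE of alpha is 0.002.

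| Assumed r | Reported / empirical SE, no site | Actual alpha, no site | CI width without / with pooled site |
|---|---|---|---|
| 0 | 0.985-1.011 | - | 0.984-0.996 |
| 0.10 | 1.018-1.048 | 0.041-0.047 | 1.011-1.037 |
| 0.20 | 1.058-1.097 | 0.032-0.041 | 1.035-1.086 |

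At r = 0, adding site widens the CI by 1/0.996 - 1 = 0.4% to 1/0.984 - 1 = 1.6%.

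**Cross-checks.**

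- A separately coded simulation (3,000 runs per setting, 5 or 10 sites, 20% dropout, sites not pooled) gave SE ratios without site of about 1.03-1.05 at r = 0.10, 1.04-1.09 at 0.20 and 1.08-1.13 at 0.30. With site in the model, alpha was 0.041-0.055 in the site-blocked settings.
- Under unstratified randomisation the ratio stayed at 0.98-1.03. The excess SE therefore comes from blocking on site and then omitting it.
- Power for an assumed effect of 0.9 SD (5 sites, blocks of 3), without and with site, was 0.78 and 0.77 at r = 0, 0.79 and 0.81 at 0.10, and 0.82 and 0.86 at 0.20.
- The simulations above model one visit. In a two-visit unstructured model (800 runs per setting, 5 or 8 sites, blocks of 3, 60 of 75 analysed), the CI without site was 1.4-3.1% wider at r = 0.10 and 3.5-7.8% wider at 0.20. The one-visit stand-in does not materially overstate the effect.

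**The case against.** **The harm is small and on the safe side.** The estimate is unbiased, the error is conservative, the trial is exploratory, and a few percent of CI width is unlikely to change a decision. This stands, and it limits the weight of the point without removing it.

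**The size is assumed.** Nothing in the documents supports 10% or 20%. Adjustment for baseline limits the effect of stable site differences in level, and PSP-rating evaluators are restricted to trained neurologists; both may reduce site variance in change. This stands. The true figure could be near zero, in which case adding site costs a little precision.

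**The stratum is inferred.** Protocol 6.3 refers to a randomisation plan that is not among these documents and may name it. This is fair, and the first step of the fix is to check that plan. The SAP still needs to say how a stratified randomisation is handled.

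**Protocol and SAP agree on the covariates.** The model is pre-specified and consistent, so replacing it as primary is not strictly necessary. This stands, and a pre-specified site-adjusted sensitivity analysis would be enough.

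**Pooling small sites merges strata.** A pooled model does not match the design exactly. That is true, but the CI ratios in the table already include pooling.

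**Conclusion.** The point holds. On the evident reading, allocation is balanced within site, and no planned efficacy analysis takes account of it. The consequence is possible loss of precision and power, without bias and without excess false positives. If site accounts for 10-20% of the variance in change, the reported SE is 2-10% too large, actual alpha is 0.032-0.047 in place of 0.05, and the CI is 1-9% wider than with pooled site in the model. If sites do not differ, nothing is lost. These figures rest on three things: site being the stratum, the assumed site numbers, block sizes and variance shares, and dropout at random. The gain is modest but nearly free, so the change should be made before database lock.

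**What to change.** 1. In SAP 5.3, name the randomisation stratum or strata, confirmed against the randomisation plan, and state whether each enters the efficacy models.
2. If site is the stratum, add pooled study site as a fixed categorical effect in 9.1.2, 9.2.1.2 and 9.2.2.2, and in the overall models that refer to 9.2.2.2. Fix the pooling rule no later than the blind meeting, for example one combined level for sites with fewer than 6 FAS subjects.
3. Record this in SAP 3.5 as a departure from protocol 11.2.3 and 11.2.8, and keep the model without site as a sensitivity analysis in section 12. If the sponsor prefers the protocol model as primary, reverse the two roles.
4. Leave site out of the within-type models of SAP section 11. If 30% of 60 analysable subjects are parkinsonian type (assumed), that is 18 subjects with 6 fixed terms per visit: 18 - 6 - 4 = 8 residual degrees of freedom with 5 sites, and 18 - 6 - 11 = 1 with 12.

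**Cost.** A SAP edit with an entry in 3.5, or a protocol amendment. No new data are needed, because the site number is part of each randomisation number. The model loses one degree of freedom fewer than the number of pooled sites, and the CI is about 0.4-1.6% wider if sites do not differ.
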